#### **Background Information:**

Skin cancer is by far the world's most common form of cancer – with more diagnoses annually than breast, prostate, lung, and colon cancers combined. Every year in Canada over 80,000 cases of skin cancer are diagnosed, over 7,200 of which are Melanoma, the most deadly form of skin cancer. It is estimated that in 2017, over 1250 Canadians have died of Melanoma.

The incidence of melanoma in Canada is on the rise in both men and women. In women the incidence of melanoma has increased by 2.8% between 2001 and 2010, an annual percentage

change surpassed only by thyroid cancer. As mortality rates for almost all other forms of cancer decrease – the age-standardized mortality rate of melanoma is on the rise. Melanoma is the number one cancer killer of women aged 25 to 30.

As a whole, 5-year age-standardized survival rates for melanoma have been reported as high as 88%. When discovered early, melanoma can usually be cured with surgery alone, but once it metastasizes therapeutic options are limited. 5-15% of patients with melanoma will progress to stage IV MM. MM is one of the most aggressive malignancies, with 5-year survival rates of advanced disease between 5-23%, depending on the location of tumor dissemination. Although several new therapeutic interventions for metastatic melanoma are undergoing clinical trials, for the foreseeable future MM is a disease characterized by a worrying rate of mortality, and treatments of questionable efficacy.

Given the paucity of effective therapeutic interventions for MM, successful strategies in treating melanoma will include therapies or therapeutic adjuvants which limit, or altogether prevent metastases.

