This study is a randomized, controlled, double-blind study. Patients with highly suspicious pigmented lesions will be randomly assigned by an algorithm to one of two groups: 1) treatment group patients will be treated intralesionally with IL-2 (Proleukin (Aldesleukin), Novartis Pharmaceuticals Canada Inc.) at a dose of 500,000 International Units (IU) (0.1ml) for 2 treatment cycles 1 week apart (Day 1 and Day 8) Figure 1; 2) control group patients will be treated intralesionally with sterilized sodium chloride (0.9%, m/v) (0.1ml) Figure 1. Randomization will be done at the pharmacy for each patient (generated by a Random Block algorithm). IL-2 (Proleukin) will be obtained from the Provincial Drug Distribution Program by the pharmacy, paid for by [name] research services account (please see budget attached). The pharmacy will prepare either IL-2 treatment (supplied as 1 x 0.8ml (4 million units) or injectable placebo (0.9% sodium chloride) supplied as 0.8ml). The syringes will be prepared by following aseptic technique in a biohazard hood. A 22-million unit vial of IL-2 will be reconstituted with 1.2ml of sterile water for injection and mixed gently. After drawing up 3.2ml of 5% dextrose in water and transferring to the IL-2 vial, the resulting concentration will be 5 million units/ml. 0.8ml of the IL-2 solution will then be drawn into a 3ml syringe. Expiry time of the reconstituted solutions is 48 hours at 4C. The pharmacy will assign a codified ID which will be provided along with the syringe with the patient name labeled as "Interleukin-2/Placebo" (thus blinding study to clinician and patient). As a pilot study, the principle of the design is to test the feasibility of proceeding to a larger and more expensive trial following the methodology and protocol proposed. As such there will be a minimum of 20 (10 treatment, 10 placebo) participants (up to a maximum of 60). It is estimated that statistical significance will be reached with 20 patients, however it is not reached after 20 patients, an additional 10 (5 treatment, 5 control) patients will be enrolled. If significance is still not reached after 30 patients, an additional 10 patients will be enrolled and so on up to a maximum of 60 patients. If after 60 patients, significance is not achieved then further recruitment under the current protocol would not be logical and therefore the methodology would need to be revised or study discontinued.

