On Day 1 (first treatment) and 15 (excisional biopsy), all patients will have blood (4 vials) and urine (25-50 ml) samples taken. Local reactions to injections will be monitored for non-specific signs such as bleeding, arythema, infection, or irritation. We don't anticipate specific changes in the pigmented lesion related to the injection in this short time period, however all changes will be noted.

On Day 15, following the second intralesional injection an excisional biopsy will be performed following standard surgical techniques, as follows: ellipse of skin encompassing the pigmented lesion extending into the subcutaneous fat will be performed to achieve a grossly clear but narrow margin of excision. This small defect will be closed primarily with interrupted sutures. The biopsied specimen will be subsequently evaluated using standard histological techniques to confirm diagnoses, assess margin status (clear or involved) and depth of lesion invasion. The depth of lesion invasion will dictate the extent of subsequent surgical excisions and margin selection according to standard National Comprehensive Cancer Network (NCCN) guidelines. Pre-biopsy intralesional injections of 0.1ml into the lesion will not alter dimensions or architecture of the lesion or impact the extent the subsequent biopsy required. Lesions that are felt to be too large for closure without tissue manipulation or creation of flaps, will be biopsied using a punch biopsy sampling technique whereby 4mm diameter discs of tissue from representative areas of the lesion will be taken to confirm the diagnosis and the depth of invasion. The depth of invasion will dictate the extent and complexity of subsequent surgery required to remove the lesion and achieve clear margins according to NCCN guidelines. The biopsied specimen will be processed as follows: using a 22G needle a fine needle aspiration biopsy will be performed (the needle will be passed through the center of the lesion two times) for RNA analysis. The remainder of the tissue will be sent to pathology for standard histological assessment. The pathologist will also report the extent of observed tumor infiltrating lymphocytes (TILs) associated with treatment compared to control injections. Blood and urine will be assessed using metabalomic and proteomic methods to assess systemic immune response to treatment.

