#### Analysis of Data

#### Outcome measure/study objectives:

Assessment of Number of Patients Needed to Obtain Significance [**Time Frame: 1 year**] – Data will be analyzed in order to achieve a statistically significant differentiation between treatment and control outcomes in study measures including tumor infiltrating lymphocytes (TILs) and circulating immunomodulators.

Assessment of Metastasis [**Time Frame: 5 years**] - All patients will receive assessments every 4 months for 2 years and then biannual assessments for years 3-5 after the initial intervention to assess disease metastasis in treatment and control groups. Both number of new metastases (integer value) and thickness (mm) will be measured as a part of this assessment.

Sub-Study Outcome Measure:

Assessment of RNA genetic profile **[Time Frame: 5 years]** - RNA analysis of excised tissue will be compared to unaffected patient tissue obtained from the clear margins of the excisional biopsy to assess genetic changes resulting from the melanoma and treatment/placebo injections. RNA analysis will occur at [name] laboratory (Sir Charles Tupper Medical Building, 11F11) at Dalhousie University.

Assessment of Systemic Immune Response: Proteomic Analysis [**Time Frame: 5 years**] - Proteomic analysis will be conducted on blood samples to assess systemic immune response to both treatment and control groups. Serum collected from patient blood samples will be used for proteomic analysis to assess protein expression, including circulating immunomodulators (cytokines and chemokines) before, and after, treatment. Proteomic analysis will occur at Dalhousie's Proteomics and Mass Spectrometric Core Facility located in the Life Sciences Research Institute. This study may serve to help develop diagnostic protocols and methods of assessing response to treatments.

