#### How will the data be analyzed:

All study practices and statistical methods are based on the International Conference on Harmonization (IHC) document "Statistical Principles for Clinical Trials." Data will be summarized by treatment group. Baseline characteristic, safety outputs and a total overall column will be included to summarize all subjects. For all baseline, demographic, safety and efficacy outputs data will be summarized by treatment group. In summary tables of continuous variables, the minimum and maximum statistics, the arithmetic mean and median, the 95% confidence interval, standard deviation, and standard error will be presented will to the same number of decimal places as the original data. In summary tables of categorical variables, counts and percentages will be used. The denominator for each percentage will be the number of subjects within the population treatment group unless otherwise specified. All hypothesis testing will be carried out at the 5% (2-sided) significance level unless otherwise specified. P-values will be rounded to three decimal places. P-values less than 0.001 will be reported as <0.001 in tables.

The treatment label for all tables, listings and figures will be:

Treatment	Label
2 treatment cycles of	IL-2
500,000 IU of IL-2 in 0.1	Treatment
mL	
0.1 mL of sterile saline	Placebo
(0.9% m/v)	
All Treatments	Total

Where that any of the statistical methods described herein prove unsuitable during analysis, more appropriate methods will be used. All changes in methodology will be documented in the clinical study report. Additional ad-hoc analyses may be conducted as deemed suitable.

Subject inclusion/exclusion criteria will be determined at baseline visit, and subjects who do not meet all criteria will not be entered into the study. Those subjects deemed eligible to participate will be allocated a 3-digit number at randomization prior to the initial treatment. If a subject is discontinued at any time after entering the study, the Investigator will ensure this does not affect the patient's standard of care. At the patients request all unused biological samples (blood, urine, and core biopsies) will be immediately destroyed. The reasons for withdrawal will be recorded on the CRF and will be included in the final report. Failure to complete both (2) treatment cycles will result in patient removal from the trial.

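### Showing summary statistics at raw-data precision could print the integer metastasis count as mean 0 in both arms, even when the arms differ

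*Combined protocol and SAP*

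**What the plan says.** The section How will the data be analyzed lists what is to be shown for numeric data: "In summary tables of continuous variables, the minimum and maximum statistics, the arithmetic mean and median, the 95% confidence interval". The same sentence goes on to two more statistics and then fixes the precision for the whole list: "standard deviation, and standard error will be presented will to the same number of decimal places as the original data". No extra decimal is allowed for derived statistics. The next sentence treats the other data type differently: "In summary tables of categorical variables, counts and percentages will be used". P-values have their own rule, three decimals, whatever the precision of the data.

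Under Outcome measure/study objectives, the Assessment of Metastasis reads: "Both number of new metastases (integer value) and thickness (mm) will be measured as a part of this assessment". The plan does not say whether the count is to be tabulated as continuous or as categorical.

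**The concern.** A whole-number variable has zero decimals, so under this rule its mean, SD, SE and confidence limits are rounded to whole numbers. For a rare event the mean count per patient lies well below 0.5 and rounds to 0. The efficacy table for metastasis could then show the same zeros in both arms when the underlying data differ, and a reader could not recover the estimate or its uncertainty from those entries. Any other outcome recorded in whole numbers and summarised as continuous would be over-rounded in the same way.

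**Working it through.** The plan states no figure for this point, so there is nothing to reproduce. The rule is applied directly.

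**Inputs**
- Arm size n: 10 per arm at the planned minimum; 30 per arm at the maximum of 60 if allocation stays equal (Research Plan).
- Rate p: "5-15% of patients with melanoma will progress to stage IV MM" (Background Information). This describes melanoma patients in general and is not an assumption of this trial. It is used as 5%, 10% and 15% in both arms.
- Metastases per affected patient, k: not in the document. Assumed; k = 1, 2, 3 and 5 are shown.

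**Formulas.** With x of n patients affected and k metastases each: mean = kx/n; SD = k·√[x(n−x)/(n(n−1))]; SE = SD/√n; 95% CI = mean ± t·SE, with t = 2.262 (n = 10) or 2.045 (n = 30). Each result is then rounded to zero decimals.

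**An example in which the arms differ.** 0 of 30 versus 9 of 30, k = 1. In the affected arm:
- mean = 9/30 = 0.30
- SD = √[9×21/(30×29)] = 0.466
- SE = 0.466/√30 = 0.085
- CI = 0.30 ± 2.045×0.085 = 0.13 to 0.47

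All five numbers print as 0, the same as in the arm with no events. Fisher's exact two-sided p = 0.002. The table would set identical zeros beside that p-value.

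**Where the zeros stop, k = 1.**
- n = 10, 1 affected: mean 0.10, SD 0.32, SE 0.10, CI −0.13 to 0.33. All print 0.
- n = 10, 2 affected: mean 0.20, SD 0.42, SE 0.13, CI −0.10 to 0.502. The upper limit prints 1.
- n = 10: the mean itself first reaches 0.5 at 5 affected.
- n = 30, 10 affected: upper limit 0.512, prints 1. So 9 is the largest number that leaves every one of these statistics at 0.

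**How likely, k = 1.** An arm mean prints 0 if x ≤ 4 (n = 10) or x ≤ 14 (n = 30). Mean, SD, SE and CI all print 0 if x ≤ 1 (n = 10) or x ≤ 9 (n = 30). The binomial probability is squared for two arms:

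| | p = 5% | 10% | 15% |
|---|---|---|---|
| Both means print 0, n = 10 | 0.9999 | 0.997 | 0.980 |
| Both means print 0, n = 30 | 1.00 | 1.00 | 1.00 |
| All statistics print 0 in both arms, n = 10 | 0.84 | 0.54 | 0.30 |
| All statistics print 0 in both arms, n = 30 | 1.00 | 0.999 | 0.98 |

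**Sensitivity to k: probability that both means print 0.**

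| | p = 5% | 10% | 15% |
|---|---|---|---|
| k = 2, n = 10 | 0.98 | 0.86 | 0.67 |
| k = 3, n = 10 | 0.84 | 0.54 | 0.30 |
| k = 5, n = 10 | 0.36 | 0.12 | 0.04 |
| k = 5, n = 30 | 0.66 | 0.17 | 0.02 |

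**The case against.** The strongest reply is that this is only a display rule, that it may not reach the metastasis count at all, and that its effect is not certain.

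- **Scope.** The rule covers continuous variables. A count shown as categorical gets counts and percentages and escapes it. This stands as a condition on the point, but the plan does not assign the count to either type.
- **The outcome does not vanish.** A reader might infer that every summary of metastasis would read 0. That is wrong: the same sentence of the plan also prints the maximum, which shows at least 1 in any arm with an event.
- **Zeros are not assured.** At 10 per arm and k = 1, the all-zero table needs no more than one affected patient in each arm, so the difference it hides is at most one patient; at a 15% rate it is the less likely outcome. With several metastases per affected patient, nonzero means become likely. This stands, and it is why the point says could rather than would.
- **Inference is untouched.** Tests are run on the data at the stated 5% two-sided level, p-values carry three decimals, and the decision to keep enrolling rests on significance. This stands in full.

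A reader might also infer that rounding would distort the SD of a tumor infiltrating lymphocyte grade, and so mis-size the later trial that the first major aim looks toward. The document does not support that. It says only that "The pathologist will also report the extent of observed tumor infiltrating lymphocytes (TILs) associated with treatment compared to control injections", with no scale or unit. It describes no sample-size calculation based on an SD, and nowhere says that calculations would use rounded table entries.

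The clause allowing unsuitable methods to be replaced is a weak defence, since it speaks of statistical methods and not expressly of display precision.

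**Conclusion.** The point holds in conditional form. If the metastasis count is tabulated as a numeric variable, the stated rule could print its mean as 0 in both arms, and often the SD, SE and confidence limits as well, even when the arms differ as much as 0 of 30 versus 9 of 30. With one metastasis per affected patient and a 5-15% rate, both means print 0 with probability at least 0.98 at either arm size; the fully zero table has probability 0.30 to 0.84 at 10 per arm and 0.98 or more at 30 per arm. These figures rest on an assumed number of metastases per affected patient and on a background rate. Enrolment is on clinical suspicion, so the rate among all participants could differ from it. The defect lies in the reporting of estimates and their uncertainty, not in the tests. It is minor, but it follows from a rule that the plan states, not from a missing detail.

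**What to change.** Replace the decimal-place rule with one sentence: mean, median and confidence limits to one more decimal than the raw data; SD and SE to two more; minimum and maximum as collected. The 9-of-30 arm would then read mean 0.3, SD 0.47, SE 0.09, CI 0.1 to 0.5.

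Also tabulate the metastasis count as a frequency table by arm: patients with 0, 1, and 2 or more, with percentages. For a rare count this is the clearer display. Extra decimals alone would give 1 of 10 affected as mean 0.1 with CI −0.1 to 0.3, a negative limit for a quantity that cannot be negative.

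The cost is a sentence or two in the analysis section and one added table. No change to data collection, sample size or testing is needed.

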Assessment of Systemic Immune Response: Metabolomic Analysis [**Time Frame: 5 years**] - Metabolomic analysis will be conducted on urine samples to assess systemic immune response to both treatment and control groups. All tumor and tissue produce by products in waste that are excreted by the kidneys. Urine samples can be evaluated using techniques, such as Mass Spectrometric, to determine if biological compounds can be identified in association with the presence of a malignant process that would not be produced by normal tissue. Metabolome analysis will occur at Dalhousie's Proteomics and Mass Spectrometric Core Facility located in the Life Sciences Research Institute. This study may serve to help develop diagnostic protocols and methods of assessing response to treatments.

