Data resulting from our RNA, metabolomic and proteomic studies will be analyzed using specific statistical software available to us at Dalhousie University, including Bio-Rad qPCR machine and CFX manager statistical software for RNA analysis, and liquid chromatography-tandem mass spectrometry (LC-MS/MS) systems (QTRAP5500 by ABSciex) and bioinformatic analysis for metabolomic and proteomic studies.

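### No multiplicity control is specified for the proteomic, metabolomic and RNA sub-studies, so the default 5% level applies to an unstated number of features and the Aim 3 findings would have no known error rate

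*Combined protocol and SAP*

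**What the plan says.** The general rule, under the heading How will the data be analyzed, is "All hypothesis testing will be carried out at the 5% (2-sided) significance level unless otherwise specified". The same section allows unsuitable methods to be replaced, with the change documented, and allows ad-hoc analyses.

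For the sub-studies it names tools rather than methods: "including Bio-Rad qPCR machine and CFX manager statistical software for RNA analysis", and mass-spectrometry systems "and bioinformatic analysis for metabolomic and proteomic studies". The bioinformatic analysis is not described.

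The scope comes from Outcome measure/study objectives. Serum goes to "proteomic analysis to assess protein expression, including circulating immunomodulators (cytokines and chemokines"). Urine is searched by mass spectrometry for compounds associated with malignancy. RNA from the lesion is compared with the patient's own clear-margin tissue, to look at changes due to the melanoma and to the injections. Of both the proteomic and the metabolomic work the plan says: "This study may serve to help develop diagnostic protocols and methods of assessing response to treatments". Aim 3, under Hypothesis, asks whether specific immune modulators differ between the arms, but does not list them.

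On size, the Research Plan says "there will be a minimum of 20 (10 treatment, 10 placebo) participants (up to a maximum of 60").

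**The concern.** These platforms can return many measurements per patient, and the trial may have as few as 10 patients per arm. A 5% level applied to each comparison lets chance findings accumulate with the number of comparisons. Since that number is not given, nobody can say beforehand, or from the report, how far to trust a list of significant features.

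At stake is the answer to Aim 3 and, more tentatively, the later diagnostic work that the plan mentions. The reporting rule makes repair afterwards harder. P-values below 0.001 are shown only as less than 0.001, whereas with 300 features the smallest Benjamini-Hochberg threshold at a 10% false discovery rate is 0.10/300 = 0.00033. A reader could not reliably apply the correction from the published tables.

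**Working it through.** **The plan's own figure.** The Research Plan states "It is estimated that statistical significance will be reached with 20 patients", with no endpoint, effect size, SD, power or number of tests. It cannot be reproduced. Solving backwards for one two-sided 5% t-test with 10 per arm, 80% power needs a difference of 1.32 SD and 90% power needs 1.53 SD. That concerns a single test and says nothing about many.

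**Inputs from the documents.** Level 0.05 two-sided; 10 per arm minimum, 30 per arm at the maximum of 60 with equal allocation.

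**Assumed inputs, because the documents are silent.** Number of features m; share truly changed π, 1% to 50%; standardised difference d, 0.5 to 1.5; independent, normally distributed features; one analysis, two-arm comparison.

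**Step 1: nothing truly changed.** Expected false positives = 0.05 × m. Chance of at least one = 1 − 0.95^m.

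| m | Expected false positives | Chance of at least one |
|---|---|---|
| 5 | 0.25 | 23% |
| 20 | 1 | 64% |
| 100 | 5 | 99.4% |
| 300 | 15 | >99.9% |

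**Step 2: some features truly changed.** False share of the significant list = (1 − π) × 0.05 / [(1 − π) × 0.05 + π × power], a ratio of expected counts. Noncentral-t power at 10 per arm is 18.5% (0.5 SD), 56.2% (1 SD) and 88.7% (1.5 SD).

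| Share changed | 0.5 SD | 1 SD | 1.5 SD |
|---|---|---|---|
| 1% | 96% | 90% | 85% |
| 5% | 84% | 63% | 52% |
| 10% | 71% | 44% | 34% |
| 20% | 52% | 26% | 18% |
| 50% | 21% | 8% | 5% |

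For example, 5% changed by 1.5 SD gives 0.0475 / (0.0475 + 0.0443) = 52%. The list is more than half false only if the changed share is below 21.3% (0.5 SD), 8.2% (1 SD) or 5.3% (1.5 SD).

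**Step 3: more patients.** At 30 per arm over the same effect sizes, the false share is 49% to 67% with 5% changed and 31% to 49% with 10% changed. Even perfect power leaves 0.0475 / (0.0475 + 0.05) = 49% in the first case, so enrolling to the maximum does not remove the problem.

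**Step 4: what adjustment does.** Assume 300 features, 15 truly changed, 10 per arm. Unadjusted false hits are expected to be 285 × 0.05 = 14.3. The adjusted results are by simulation.

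| Effect | Unadjusted true hits | Benjamini-Hochberg 10%: true / false | Screen empty |
|---|---|---|---|
| 1.5 SD | 15 × 0.887 = 13.3 | 7.2 / 0.9 | under 1% of runs |
| 1 SD | 15 × 0.562 = 8.4 | 1.1 / 0.3 | roughly 40% of runs |

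**The case against.** The strongest reply is that the documents describe no feature-by-feature testing. The undefined bioinformatic analysis might include a correction, and the plan allows better methods to be substituted. That stands against any statement that every feature will be tested at an unadjusted 5%, which a reader might infer. It does not fill the gap: a method not written down is not specified, so the default level governs, and any correction would be chosen with the data in hand.

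Second, the panels may be small. Aim 3 speaks of specific modulators, and qPCR suggests a limited gene list. This is fair, and the documents do not settle it. But the chance of at least one false positive is already 23% with 5 features and 64% with 20.

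Third, this is a pilot, the omics work is called a sub-study, and diagnostic use is put tentatively, for proteomics and metabolomics but not for RNA. No feature list is promised. All of this stands and limits the downstream harm. It also means that an explicit exploratory label would be natural; the plan does not give one.

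Fourth, 10 per arm is a minimum, and the lesion-versus-margin RNA contrast is within patients, so the two-arm figures do not describe it.

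Finally, adjustment at this sample size can remove nearly everything. That is correct, and it argues against making an adjusted screen the only route by which a feature can be reported.

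**Conclusion.** The concern holds as an omission. The only operative rule is an unadjusted two-sided 5%, and no multiplicity control, feature panel or exploratory label is given for the three platforms.

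A reader might go further and infer that the Aim 3 results would be largely chance findings. The documents do not support that. The feature count, the effect sizes and the share truly changed are all missing, and the false share at 10 per arm runs from about 5% (half of features changed by 1.5 SD) to about 96% (1% changed by 0.5 SD). With 20% changed by 1 SD it is 26%. The supportable conclusion is that the error rate is unknown and uncontrolled.

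The figures assume independent, normal features and a single analysis. Correlation between features changes the chance of at least one false positive but not the expected number. The possible repeat analyses as enrolment grows are a separate matter and are not counted here. As this is a sub-study of a pilot, the change should be made, but the point does not undermine the trial as a whole.

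**What to change.** Add one paragraph to the section How will the data be analyzed, before any unmasking:

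- List the few cytokines and chemokines tied to the Aim 3 hypothesis as their own small family, and control multiplicity within it (for example, by Holm).
- For all other features, within each platform separately, report Benjamini-Hochberg adjusted p-values (for example, at a 10% false discovery rate) beside unadjusted estimates and confidence intervals. State how many features were tested and which contrast was used.
- Label unadjusted hits hypothesis-generating, and do not report them as established differences.
- Report sub-study p-values to enough decimal places for the adjustment to be checked.

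No new samples or visits are needed. The cost is fewer declared features. Under the assumptions of Step 4, about 7 rather than 13 true hits remain at 1.5 SD. At 1 SD about 1 rather than 8 remain, and the screen is empty in roughly 40% of runs. The small family softens this but does not remove it. With five markers, an assumed number, the strictest step is 0.05/5 = 0.01; at 10 per arm, noncentral-t power at that level is 68% for 1.5 SD and 29% for 1 SD. The unadjusted estimates and intervals stay in the report, so signals that do not survive adjustment remain available for planning the next study.

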All blood, urine, and lesion biopsy samples will be labeled with a codified number (will not contain any patient identifying information) and will be immediately transported to [name] laboratory (Sir Charles Tupper Medical Building, 11F11) at Dalhousie University for storage. Fine needle aspiration of excised samples will be assessed for tumor genetic and epigeneitic profile (Figure 2). Blood and urine will be assessed for proteomic and metabolomic profiles, respectively (Figure 2).

A database containing patient IDs and codified numbers will be restricted to the office of [name] (11th floor, VG). This is a locked office, and the data will only be accessible to the investigators named on this application. This database for will contain patient IDs, and info on disease status, treatment/control, follow up visits, and sample analysis – only info pertinent to the outcome measures. All sample data will be assessed using codified descriptors and will contain no patient ID info. Once the RNA, proteomic, metabolomic and pathology data has been analyzed, unmasking treatment and control groups will be conducted at the VG office of [name], by the named investigators. If the data reaches statistically significance, the study will not accept any more patients, if not, a further 10 patients will be incorporated – to a maximum of 60 patients. Any publications of study results will be completed devoid of any information that could be used to identify patients included in the study.

All study participants will receive biannual assessments for 5 years after the initial intervention to assess disease progression, or the development of new melanoma, to compare between both treatment and control groups. There is no standardize test or measurable biomarker to assess established or lasting immunity. This aspect of the study is identical to the patient assessment conducted as per standard of care for melanoma patients. Again, any publications of study results will be completed devoid of any information that could be used to identify patients included in the study.

	Interleukin 2 Treatment Group				
Interleukin-2 Treatment Group		Placebo Treatment Group			

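### No between-group test is fixed before unmasking, and methods may be changed during analysis, so from the second look the stop/continue test can be chosen by people who know earlier arms and results

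*Combined protocol and SAP*

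**What the plan says.** Under *How will the data be analyzed*, the plan lists summary statistics and rounding rules and sets one error level: "All hypothesis testing will be carried out at the 5% (2-sided) significance level unless otherwise specified". It names no between-group test, model or primary variable. The paragraph after it, on laboratory software and instruments, adds none.

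The same section then makes three statements in a row:
- On replacing a method, it says: "Where that any of the statistical methods described herein prove unsuitable during analysis, more appropriate methods will be used".
- On recording such a change, the only place it requires is the final study report.
- On further unplanned work, the permission is open-ended: "Additional ad-hoc analyses may be conducted as deemed suitable".

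No trigger, fallback test or deadline is attached to a change, and nothing says which analysis counts if several are run.

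Under *Research Plan*, the order of events is: "Once the RNA, proteomic, metabolomic and pathology data has been analyzed, unmasking treatment and control groups will be conducted", by the named investigators. The decision follows: "If the data reaches statistically significance, the study will not accept any more patients, if not, a further 10 patients will be incorporated". The first decision comes at 20 patients (10 per arm) and later ones after each further 10, to a maximum of 60. Blinding is described for clinician and patient only. The investigators' database holds treatment or control status, and no separate masked analyst is described.

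**The concern.** A clause that lets an unsuitable method be replaced is common and would be minor alone. Here it sits beside three other features: no test is named, the investigators who unmask also take the decision, and recruitment stops when significance is reached. The first choice of test is therefore as open as any replacement. By the second look, those who may change the method know the arms and results of the first 20 patients. Nothing prevents a replacement or ad-hoc analysis from being the one that stops the trial.

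Choosing among reasonable analyses with results in view raises the false-positive rate of a nominal 5% test. This is separate from the effect of repeated looks and would remain if the looks were corrected. A false positive would stop this pilot early and support a larger trial.

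**Working it through.** **Inputs from the documents.** Two-sided 5% level; 1:1 allocation; looks at 20, 30, 40, 50 and 60 patients, so n = 10, 15, 20, 25 and 30 per arm. Blood is taken on Days 1 and 15, so an immunomodulator has a before and an after value. TILs come from the Day 15 biopsy only; no Day 1 tissue is taken.

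**Assumptions.** No treatment effect; the menus of analyses below; normal data for the immunomodulator with Day 1–Day 15 correlation ρ of 0.3, 0.5 or 0.7; normal or log-normal data for TILs, whose scale the plan does not give. The lowest p-value is always taken, at every look, so each best-of figure is a ceiling for its menu.

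**Step 1: the plan's own figure.** Its only error figure is 5%. One fixed analysis of normal immunomodulator data, at one look with 10 per arm, gives 4.9–5.1% in simulation, so the nominal level holds.

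**Step 2: looks alone, one fixed test.** With Z_k the cumulative standardised difference at look k, the error is P(max |Z_k| > 1.96). Cumulatively by look it is 5.0%, 7.7%, 9.7%, 11.4% and 12.7%. This part is not due to choice of method.

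**Step 3: TILs (one value per patient; 40,000 replicates per distribution).**

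| Menu | One look | Five looks |
|---|---|---|
| Rank test only | 4.3–4.5% | 11.9–12.3% |
| Better of t-test and rank test | 5.2–5.8% | 15.0–15.6% |
| Best of five (t, rank, t on logs, two Fisher cuts) | 6.5–6.9% | 18.6–19.7% |

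**Step 4: one immunomodulator (100,000 replicates per ρ).** Three contrasts between arms are tested:
- Day 15: mean difference d15, t-test on 2n − 2 degrees of freedom.
- Change: d15 − d1, t-test on 2n − 2 degrees of freedom.
- Adjusted: d15 − b·d1, with b the pooled within-arm slope, on 2n − 3 degrees of freedom.

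A false positive is counted if the smallest of the three p-values is below 0.05.

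| ρ | Best of three, one look | One fixed contrast, five looks | Best of three, five looks |
|---|---|---|---|
| 0.3 | 9.2% | 12.9–13.0% | 22.5% |
| 0.5 | 9.6% | 12.9–13.1% | 23.5% |
| 0.7 | 10.0% | 12.9% | 24.3% |

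Over five looks, free choice adds about 22.5 − 13.0 = 9.5 points at ρ = 0.3 and 24.3 − 12.9 = 11.4 points at ρ = 0.7, beyond the effect of the looks.

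**The case against.** **Timing.** A reader might infer that the test is chosen with the arms known from the first look. The documents do not establish this. The Research Plan puts unmasking after the laboratory and pathology data have been analysed, so the first method may be settled while masked. The sentence is ambiguous, because a significance decision by arm needs the allocation or coded groups, and no coded-group comparison is described. The objection stands for the first look and fails from the second.

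**Size.** A reader might also apply 9–10% to the trial as a whole. It cannot apply to TILs, the first-named measure: with no Day 1 tissue there is no change score or baseline adjustment. Much of the immunomodulator figure reflects an undefined outcome variable rather than the replacement clause. This stands, and the two outcomes are kept apart above.

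**Intent.** The outcome section's "Data will be analyzed in order to achieve a statistically significant differentiation between treatment and control outcomes" might be read as a declaration that significance will be pursued. Its heading concerns the number of patients needed, and it closely follows Major Aim 1 under *Hypothesis*, which is a sample-size aim. It is not evidence of intent and need not be rewritten.

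**Routine wording.** The clause is conditional on unsuitability and carries a disclosure duty, and the section invokes the ICH statistical principles. Disclosure in the final report comes after the decision, and the general reference supplies no test. This does not answer the concern.

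**Conclusion.** The concern holds in a limited form. No comparative analysis is fixed before unmasking, methods may change during analysis, and ad-hoc analyses are not barred from the stop/continue decision. From the second look this permits a choice informed by earlier arms and results.

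The cost is small for TILs at one look and larger for an immunomodulator with before and after values, where the false-positive rate could reach about 9–10% at one look and 22–24% over five. About 13 points of the five-look figure come from the looks themselves. The single-look figures show what free choice could cost; they do not show that the first look is unmasked when the method is chosen. Choosing among several immunomodulators would add more and is not counted. All best-of figures rest on assumed menus, correlations and distributions. The plan should be changed, and doing so touches no clinical procedure.

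**What to change.** 1. Before the first unmasking, fix in a dated document one variable and one test for the stop/continue decision. Examples are a rank test for TILs, and the Day 15 value adjusted for Day 1 for any immunomodulator used. The plan names no immunomodulator, so one would have to be named.

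2. Replace the replacement-of-methods sentence under *How will the data be analyzed* with wording to this effect: *The stop/continue decision and any claim of significance use only the analysis fixed before the first unmasking. Any method changed after that date, and any ad-hoc analysis, is reported beside it as exploratory and can neither declare significance nor determine recruitment.*

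3. Leave the sample-size aim in the outcome section as it is; removing it would put that section at odds with Major Aim 1.

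Allowing later changes if they are decided from masked pooled data would not work under the present arrangements: after the first look the same investigators know the first 20 allocations. Tying the decision to the pre-fixed analysis avoids the need for a new masked role.

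The cost is a short dated document, a wording change and less freedom to change methods after unmasking. The fix removes only the part due to choice of method. With one fixed test and five looks at 5% each, the error is still about 13%, so the looks need their own adjustment.
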